15.4 Vital Signs

Vital signs and weight will be collected throughout the study; height will be measured at Screening, Week 12, and Week 104/EOT/ET. Observed vital signs including weight and BMI and the changes from Baseline at each post-Baseline visit will be summarized using descriptive statistics.

Vital sign values will be considered PCI if they meet the criteria listed in [Table 6](#). The number and percentage of subjects with post-Baseline vital signs that are PCI will be summarized at each post-Baseline visit and for overall post-Baseline. For the overall post-Baseline summaries, all post-Baseline values will be considered, including unscheduled and out of window values. Subjects with multiple PCI values for a given parameter will be counted only once for that parameter. For the by-visit summary, the numerator for the percentage is the number of subjects with a post-Baseline PCI vital sign for the given parameter and visit, and the denominator is the number of subjects with non-missing values for the given parameter and visit. For the overall post-Baseline summary, the numerator for the percentage is the number of subjects with at least 1 post-Baseline PCI vital sign for the given parameter, and the denominator is the number of subjects with non-missing Baseline and at least 1 post-Baseline vital sign for the given parameter. A listing of subjects with any PCI vital sign values will be provided.

Table 6 Criteria for Potentially Clinically Important Vital Signs

Vital Sign Parameter	Unit	Criteria			
		Observed Value	And/Or	Change Relative to Baseline	Change from Supine to Standing
Systolic blood pressure (supine or sitting)	mmHg	≥140	And	Increase of ≥20	-
		≤70	And	Decrease of ≥20	-
Diastolic blood pressure (supine or sitting)	mmHg	≥90	And	Increase of ≥15	-
		≤50	And	Decrease of ≥15	-
Pulse (supine or sitting)	bpm	≥131	And	Increase of ≥15	-
		≤50	And	Decrease of ≥15	-
Weight	kg	Not Applicable		Increase of ≥7%	-
				Decrease of ≥7%	-

15.5 **Electrocardiogram (ECG)**

ECGs are collected throughout the study at every visit. Observed values of ECG variables (e.g., heart rate, PR interval, QRS interval, QT interval, and QTc interval) and the changes from Baseline at each assessment time point will be summarized.

QTcB and QTcF will also be categorized into the following categories (msec), and the number and percentage of subjects in each category will be summarized at each visit and for the overall post-Baseline maximum:

- Observed: ≤450, 451 - ≤480, 481 - ≤500, and >500; >450; >480.
- Change from Baseline: ≤10, 11 – 30, 31 – 60, and >60; >30.

For cardiologist's interpretations, the number and percentage of subjects with ECG results that are determined as normal or abnormal will be summarized at scheduled visits. The overall post-baseline worst interpretation will also be summarized (i.e. if a subject has one or more post-baseline ECG results that is/are considered as abnormal, this subject will be counted in the abnormal category). Cardiologist's interpretations will also be summarized in a shift table. The shifts from Baseline to overall post-Baseline worst interpretation will also be presented. For the by-visit shift summary, the denominator is the number of subjects with non-missing cardiologist's interpretation at Baseline and the given visit. For the summaries of shift from Baseline to the overall post-Baseline worst interpretation, the denominator is the number of subjects with non-missing Baseline and at least 1 post-Baseline cardiologist's interpretation.

Electrocardiogram variable values will be considered PCI if they meet the criteria listed in Table 7. The number and percentage of subjects with post-baseline PCI values will be presented at each post-Baseline visit and for overall post-Baseline. For the by-visit summary, the numerator for the percentage is the number of subjects with a post-Baseline PCI ECG for the given parameter and visit, and the denominator is the number of subjects with non-missing values for the given parameter and visit. For the overall post-Baseline summary, the numerator for the percentage is the number of subjects with at least 1 post-Baseline PCI ECG for the given parameter, and the denominator is the number of subjects with at least 1 post-Baseline ECG value for the given parameter. A listing of all subjects with any PCI ECG values will be provided.

Table 7 Criteria for Potentially Clinically Important ECG Values

ECG Parameter	Unit	High PCI Criteria
QRS Interval	msec	≥120
PR Interval	msec	≥220
QTcB	msec	>500
QTcF	msec	>500
QTcB: change from baseline		>60 msec
QTcF: change from baseline		>60 msec

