5. DATA HANDLING CONVENTIONS

All data collected in the study will be listed.

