5.5 Baseline Definition

Baseline will be defined as the last non-missing assessment, including those from repeated and unscheduled measurements, before the first trofinetide dose is administered.

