15.1 Primary Safety Endpoints

The primary safety endpoints are:

- Treatment-emergent adverse events (TEAEs)
- Serious adverse events (SAEs)
- Withdrawals due to adverse events (AEs)
- Potentially clinically important changes in other safety assessments

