15.2 Adverse Events

Adverse events will be coded using MedDRA dictionary version 24.0.

An AE (classified by preferred term) will be considered a treatment-emergent AE (TEAE) if started after first dose administration and no later than last dose date + 30 days.

The event counts, the number, and percentage of subjects reporting TEAEs will be tabulated by system organ class (SOC) and PT; and by SOC, PT, and maximum severity. A subject is counted at most once per SOC and PT even if the subject has more than one TEAE. A subject is counted at most once per SOC and PT at the maximum severity for the summary by maximum severity. The display in these tables will be sorted alphabetically by SOC and then by descending subject frequency for the PTs within each SOC.

The event counts, the number and percentage of subjects with any TEAEs will also be tabulated by PT without SOCs. This table will be sorted by descending subject frequency.

Treatment-emergent SAEs, TEAEs leading to study drug withdrawn, and TEAEs related to study drug will be summarized by SOC and PT. The tables will be sorted alphabetically by SOC and then by descending subject frequency for the PTs within each SOC. In addition, the incidence of fatal treatment-emergent AEs (i.e., events that cause death) will be summarized separately by SOC and PT.

An AE listing by subject will display all events, including those which are not treatment-emergent, and will include the verbatim term in addition to the MedDRA SOC and PT. This listing will also include all relevant eCRF data associated with the event: date of onset, date

resolved, date of last dose, severity, frequency, outcome, relationship to study drug, and action taken with study drug. Separate listings will be presented for treatment-emergent SAEs, TEAEs leading to study drug withdrawn, fatal TEAEs (if any), and TEAEs related to COVID-19 infection.

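### Weight is flagged only at ±7% of one fixed pre-dose Baseline through Week 104, so later in Period B growth alone can meet the increase flag and a moderate loss after growth can miss the decrease flag

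*SAP*

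**What the plan says.** SAP 15.4, Table 6, gives two weight criteria, "Increase of ≥7" and "Decrease of ≥7" per cent, both relative to Baseline. The observed-value column is marked not applicable, so nothing but the percent change enters. Blood pressure and pulse, by contrast, must also cross an absolute limit.

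SAP 5.5 fixes the reference: "Baseline will be defined as the last non-missing assessment, including those from repeated and unscheduled measurements, before the first trofinetide dose is administered". It is not reset when Period B starts.

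SAP 15.4 applies the rule throughout: "The number and percentage of subjects with post-Baseline vital signs that are PCI will be summarized at each post-Baseline visit and for overall post-Baseline". It adds: "Subjects with multiple PCI values for a given parameter will be counted only once for that parameter". It does not say whether weight increase and weight decrease are one parameter or two.

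SAP 15.1 names this class of result among the primary safety endpoints: "Potentially clinically important changes in other safety assessments".

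Protocol 4.1 admits girls aged 2 to 4 years weighing 9 to <20 kg, and girls aged 5 years weighing 9 to <12 kg. Protocol 6.3.3 schedules weight at every visit to Visit 10 (Week 104). Off-site weights are taken when possible. Neither document sets a weight-for-age standard, a growth adjustment, or a comparison with any weight later than Baseline.

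**The concern.** These are young children followed for two years. A fixed percentage of the starting weight suits a short study. Over 104 weeks, though, growth moves the whole weight distribution away from Baseline. Two errors can follow. The increase row can fill with ordinary growth, and the decrease row can lose sensitivity, because a girl must first give back what she has gained before her loss counts.

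The direction matters. Protocol 1.5.1 names diarrhea and vomiting as the most notable tolerability issue, so weight loss is the change a safety reader would look for. Protocol 3.1.3 gives Period B the task of assessing long-term safety. At stake is whether the Period B weight rows of a primary safety endpoint can be read at face value.

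**Working it through.** The plan states no figure on this point, so there is none to reproduce. What follows is arithmetic on Table 6 and SAP 5.5, with assumptions marked.

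**Inputs.** Thresholds are 1.07 and 0.93 times Baseline (Table 6). Baseline weight W is 9 to 19.9 kg (Protocol 4.1). Time t is days since first dose / 365.25, using 84, 168, 364, 546 and 728 days for Weeks 12, 24, 52, 78 and 104. Growth rate g is not in the documents, so I solve for it or show a range.

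**Growth that meets the increase flag: g = 0.07 × W / t.**

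| Visit | W = 9 kg | W = 19.9 kg |
|---|---|---|
| Week 12 | 2.74 kg/year | 6.06 kg/year |
| Week 24 | 1.37 | 3.03 |
| Week 52 | 0.63 | 1.40 |
| Week 78 | 0.42 | 0.93 |
| Week 104 | 0.32 | 0.70 |

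For example, at Week 104 and 9 kg: 0.07 × 9 / (728/365.25) = 0.63/1.993 = 0.32.

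The largest Baseline weight flagged at an assumed growth rate is g × t / 0.07:

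- 0.25 kg/year: 7.1 kg at Week 104, below the 9 kg entry limit, so no eligible girl is flagged.
- 0.5 kg/year: 7.1 kg at Week 52 (none), 10.7 kg at Week 78, 14.2 kg at Week 104.
- 1 kg/year: 14.2 kg at Week 52, 21.4 kg at Week 78 (all).

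**Loss that meets the decrease flag.** After a fractional gain p, a loss L counts only if (1 + p)(1 − L) ≤ 0.93, that is L ≥ 1 − 0.93/(1 + p). This gives 7.0% for p = 0, 11.4% for 5%, 15.5% for 10% and 22.5% for 20%. No growth rate is assumed.

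**A 10% loss, followed through.** It misses the decrease flag once the prior gain exceeds 0.93/0.90 − 1 = 3.3%.

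- Highest measured gain above 3.3% and below 7%: no flag at any visit.
- Gain of 7% or more: the increase flag has already fired at an earlier visit.
- Gain of 1.07/0.90 − 1 = 18.9% or more: the weight after the loss still reads as an increase.

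Example: 12.0 kg at Baseline; 13.5 kg at Week 78 (+12.5%, increase flag fires); 12.15 kg at Week 104. The last step is a 10% loss, but 12.15/12.0 = +1.25%, so no flag fires at that visit.

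**When it bites.** A 10% loss from the weight reached at a given visit, W = 12 kg, as percent of Baseline = 0.90 × (12 + g × t)/12 − 1 (g assumed):

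| Loss from weight at | 0.25 kg/year | 0.5 | 1 | 2 |
|---|---|---|---|---|
| Week 12 | −9.6% | −9.1% | −8.3% | −6.6% |
| Week 24 | −9.1% | −8.3% | −6.6% | −3.1% |
| Week 78 | −7.2% | −4.4% | +1.2% | +12.4% |

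Values at or below −7% are flagged: three of four from Week 12, two of four from Week 24, one of four from Week 78.

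**Cost of a highest-earlier-weight reference.** I simulated 400,000 girls of 12 kg with a Baseline weight and eight later ones, independent weighing errors, and growth of 0 to 2 kg/year (all assumed). Expected girls of 15 with at least one false loss flag:

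| Error SD | Highest earlier weight | Baseline |
|---|---|---|
| 1% | 0 | 0 |
| 2% | 0.2–1.8 | 0.1–0.5 |
| 3% | 2.2–8.6 | 0.9–3.1 |

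The upper end of each range is the no-growth case. In the same setting with 2% error, 97% of girls growing 1 kg/year, and all growing 2 kg/year, already carry an increase flag by Week 78.

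**The case against.** A reader might infer that weight losses in Period B vanish from the PCI output. The documents do not support that. Any girl who first gained 7% or more is in the overall PCI count and the PCI listing; what is wrong is the direction under which she appears. For a 10% loss, only a prior gain of more than 3.3% and below 7% leaves no flag at all. Large losses still meet the decrease flag, at the thresholds shown.

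A reader might also infer that the rule fails across Period B. It does not: most moderate losses soon after Week 12 are still caught unless growth is fast.

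There are other safeguards. SAP 15.4 summarizes weight and BMI change by visit. SAP 5 states "All data collected in the study will be listed". Protocol 7.4.1 requires all observed and reported adverse events to be recorded, and SAP 15.2 says "The event counts, the number, and percentage of subjects reporting TEAEs will be tabulated by system organ class (SOC) and PT". SAP 18 provides for DSMB review. The trial has about 10 to 15 girls, so individual weights can be read, and table layouts sit in separate specifications that may already split the two directions.

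All of this lowers the stakes and stands. It does not correct the PCI table. The weight and BMI summaries use the same fixed Baseline, and a current height exists after Screening only at Week 12 and Week 104/EOT/ET. A loss after growth would have to be found by hand in the listings or depend on an adverse event report.

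Finally, how many girls would be affected cannot be established. Growth rates are not given, and Protocol Appendix A lists growth retardation as a supportive feature in its diagnostic criteria for Rett syndrome. That is right, and it is why the result is stated as what can happen.

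**Conclusion.** The point holds as a minor-to-moderate reporting weakness, mainly from Week 52 and earlier only with fast growth. The loss thresholds follow from the SAP's own rule without any growth assumption. That growth alone triggers the increase flag is conditional on growth reaching the tabulated rates. The detection pattern over time and the false-flag figures rest on assumed growth, a 12 kg Baseline and, for the latter, assumed weighing error. Period A is sound in practice. The study is single-arm and descriptive (Protocol 9.2), and no hypothesis test or treatment decision depends on the flag. The consequence is confined to how the Period B weight rows of a primary safety endpoint are read.

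**What to change.** Reporting only, with no new weighings and no change to clinical management:

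1. Keep the existing ±7% criteria against Baseline.
2. State that weight increase and weight decrease are separate parameters, tabulated separately by visit and overall. This settles the once-per-parameter ambiguity.
3. Add weight-for-age z-score and its change from Baseline by visit, using a growth reference named in the SAP, and say that Period B increases of 7% or more are to be read against it.
4. As a supplementary listing, not a PCI criterion, show each weight at least 7% below the girl's highest earlier weight, with both weights and dates.

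The cost is SAP wording, some programming and one growth-reference lookup. The SAP should state three drawbacks. The highest-earlier reference produces more false flags than Baseline when weighing error is large, worst in slow growers, and off-site weighing is allowed; hence a listing with both weights, so that each entry can be judged. Without a control arm, a falling z-score cannot be attributed to the drug. The z-score needs age at each weighing, whereas SAP 9 names only age at screening.

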15.6 Physical Examination

Physical examinations are performed throughout the study at every visit in the clinic. When a study visit takes place off-site, the physical examination is not required. Physical examination results (normal, abnormal, and not done) will be summarized in a frequency table by body system and analysis visit. A listing of abnormal physical examination data will be provided.

15.7 Other Safety Endpoints

There are no other safety endpoints in this study.

16. CLINICAL PHARMACOKINETIC AND PHARMACODYNAMIC ANALYSES

For trofinetide-treated subjects, whole blood concentration for trofinetide will be listed. Whole blood concentration data for trofinetide will be summarized for the PK Analysis Set at each analysis visit using descriptive statistics. Concentrations that are below the limit of quantification (BLQ) will be displayed as “BLQ” in the data listings and imputed as 0 for computing summary statistics.

If data allow, population PK and PK/PD analyses will be performed to further characterize the PK profile and exposure response relationship of trofinetide using measures of safety and efficacy parameters. The results of population PK and PK/PD modeling will be presented in a separate report.

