6.6 Pharmacokinetic Assessments

PK blood samples will be collected at each visit during Treatment Period A.

At the Baseline visit, a PK sample is drawn predose. After the first dose of study drug is administered, two PK samples will be collected: the first, 2 hours (±15 minutes) after dosing, as close as possible to the postdose ECG, and the second, at least 1 hour after the first.

Final Version: 1.0

In addition to the two PK samples taken at Baseline, two PK samples will be taken at each subsequent visit (or upon early termination [ET]) in Treatment Period A, for a total of ten postdose PK samples over the duration of the study. At Visit 3, Visit 4, Visit 5, and Visit 6, the two PK samples will be collected at one of the following time intervals:

- 1-3 hours after dosing
- 4-7 hours after dosing
- 8-11 hours after dosing

Every subject should provide at least two PK samples from each of the specified time intervals over the course of Visits 3 through 6 (1-3 hours after dosing, 4-7 hours after dosing, and 8-11 hours after dosing). The two PK samples taken within a time interval should be collected at least one hour apart.

Pharmacokinetic samples will also be collected, if possible, at any ET visit during Treatment Period A, or the visit immediately following any SAE, or following any AE leading to discontinuation.

Pharmacokinetic samples will not be collected at the Week 104 visit, or at an ET visit during Treatment Period B.

For all scheduled PK samples (and for unscheduled samples if possible), the dates and times of administration of the study drug over the 2 days prior to and on the morning of the PK sample draw, as well as the date and time of the sample draw, will be recorded. For samples collected from subjects who experience any SAE or experience an AE leading to discontinuation, the date and time of the last dose of study drug prior to the SAE or AE leading to discontinuation will also be recorded.

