1. INTRODUCTION

This statistical analysis plan (SAP) provides a technical and detailed elaboration of the statistical analyses of efficacy and safety data for Study ACP-2566-009. This plan should be read in conjunction with the study protocol and the electronic case report forms (eCRFs).

Specifications for tables, figures, and listings are contained in separate documents. Statistical analyses for population pharmacokinetic (PK) will be presented in a separate report and therefore will not be included in this SAP.

The SAP version 1.0 is based on protocol Amendment 1, dated 30 June 2021. The SAP version 2.0 is based on protocol Amendment 2, dated 19 December 2022. Main changes include:

- added summary for number of caregivers consented and participated for optional exit interview
- added summary for number of subjects who took commercially marketed trofinetide within 30 days after study completion
- updated definition for treatment-emergent adverse events with Day 1 onset.

Note that for the caregiver optional exit interviews, following the analysis of the qualitative data, a summary report that describes the objectives, methods, participants, and results of the qualitative interviews will be prepared and reported separately from the clinical study report.

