5.6 Analysis Visit Windows

Efficacy, safety, and PK assessments will be summarized by analysis visit as presented in Table 2 below.

Table 2 Analysis Visit Windows

Analysis Visit	Study Visit	Target Study Day	Study Day Interval
Baseline (Day 1)	2	1	≤ 1
Week 2	3	15	2 – 21
Week 4	4	29	22 – 42
Week 8	5	57	43 – 70
Week 12	6	85	71 – 126
Week 24	7	169	127 – 266
Week 52	8	365	267 – 455
Week 78	9	547	456 – 637
Week 104	10	729	638 – 759

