5.6.2 Multiple Measurements within Visit Windows

In the event that more than one assessment falls within a given window, the assessment closest to the target study day will be selected for the by-visit analysis. If two assessments are equidistant from the target study day, then the chronologically last assessment will be used. Exceptions are

made for incomplete assessments, in which case, more complete assessments will be given priority.

For safety analyses where the extreme values should be selected (e.g., overall post-Baseline minimum, overall post-Baseline maximum, and potentially clinically important values), all non-missing post-Baseline values should be considered, regardless of whether the value is selected for the by-visit summaries. All assessments will be presented in data listings.

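### SAP 16 summarises whole blood concentration by visit with no split by time after dose, so each Week 2 to Week 12 row mixes near-peak and late samples (minor; one descriptive summary)

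*SAP*

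**What the plan says.** Protocol 2.1.1 lists whole blood concentration as one of two primary PK endpoints. The other is the set of population PK parameters.

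On sampling, protocol 6.6 takes one predose and two postdose samples at Baseline. After that, "two PK samples will be taken at each subsequent visit (or upon early termination [ET]) in Treatment Period A". At Visits 3 to 6 both samples fall in one of three intervals after dosing: 1-3, 4-7 or 8-11 h. Coverage is required across visits and not at each visit: "Every subject should provide at least two PK samples from each of the specified" intervals over Visits 3 to 6. The two samples should be at least one hour apart.

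On analysis, SAP 16 states "Whole blood concentration data for trofinetide will be summarized for the PK Analysis Set at each analysis visit using descriptive statistics". SAP 5.6 places PK under the visit windows explicitly: "Efficacy, safety, and PK assessments will be summarized by analysis visit as presented in Table 2 below". Table 2 has one row per visit, including a single Baseline (Day 1) row for study days up to and including 1. Where a window holds several records, SAP 5.6.2 says "the assessment closest to the target study day will be selected for the by-visit analysis", and on ties "If two assessments are equidistant from the target study day, then the chronologically last assessment will be used". Its exceptions cover incomplete assessments and extreme safety values, not PK.

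On Day 1, SAP 5.5 says "Baseline will be defined as the last non-missing assessment, including those from repeated and unscheduled measurements, before the first trofinetide dose is administered". Protocol 9.5.3 names Baseline before dosing and Baseline after dosing separately.

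SAP 1 adds a limit on what can be seen here: "Specifications for tables, figures, and listings are contained in separate documents".

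**The concern.** Concentration after an oral dose has meaning only relative to the time since that dose. Protocol 1.3.1.3 puts the peak at about 2 h. Protocol 1.3.1.6 gives an initial half-life of about 1.2 h and a terminal half-life of about 13 h. A 1-3 h sample and an 8-11 h sample therefore measure very different parts of the curve. Because girls at the same visit may be in different intervals, a visit row under SAP 16 is not a concentration at any defined time after dose. A rise or fall between rows could come from a change in the mix of sampling times.

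This is the only concentration summary that the SAP specifies, and SAP 17 repeats Section 16 in the interim analysis intended for the NDA. A reader comparing rows could take a sampling artefact for a trend over visits.

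**Working it through.** **1. Schedule.** Postdose samples per girl: 2 at Baseline + 2 × 4 at Visits 3 to 6 = 10, which reproduces the protocol's own total.

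**2. Windows.** Counting Day 1 as the first dose, the protocol visit windows are Days 12-18, 26-32, 54-60 and 85-88. Each lies inside its Table 2 window (2-21, 22-42, 43-70, 71-126). Each Week 2 to Week 12 window thus holds two scheduled samples per girl.

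**3. Is mixing likely?** There are 3^4 = 81 ways to allot three intervals to four visits, and 36 of them cover all three intervals as the protocol asks. If girls follow these 36 at random (assumed), the chance that all share one interval at a given visit is 3 × (1/3)^10 = 0.00005 for 10 girls, and smaller for 15. Mixing would be avoided only if sites sampled every girl in the same interval at a visit, which neither document requires.

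**4. Size for one sample.** Take the value at 2 h as 1 and let C(t) = (1 − B) × 2^(−(t−2)/1.2) + B × 2^(−(t−2)/13). The half-lives are the protocol's, assumed to hold at ages 2 to 5. B is the slow-phase share at 2 h; it is in neither document and is assumed to be 5% to 20%. Representative times of 2.5, 6 and 10 h are also assumed.
- B = 0.05: C(2.5) = 0.760, C(10) = 0.0420, ratio 18.1
- B = 0.10: 0.772 / 0.0741 = 10.4
- B = 0.20: 0.794 / 0.138 = 5.7

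**5. Size for visit means.** Simulation of 100,000 draws, with random compliant sequences, identical exposure at all visits and one value per girl per visit. Entries are for B = 0.05 / 0.10 / 0.20.

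| Quantity | 10 girls | 15 girls |
|---|---|---|
| Two given visits, median ratio of larger to smaller mean | 1.44 / 1.37 / 1.29 | 1.33 / 1.29 / 1.23 |
| Two given visits, share of draws at 2-fold or more | 21% / 15% / 7% | 11% / 8% / 2% |
| Extreme pair of four visits, median ratio | 2.10 / 1.94 / 1.69 | 1.83 / 1.71 / 1.54 |

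For 10 girls, moving the assumed times to 2/5/9 h or to 3/7/11 h leaves the extreme-pair median at 2.0-2.1 (B = 0.05) and 1.7 (B = 0.20). A 40% slow-phase share would lower it to 1.42.

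**6. Conditional count.** If SAP 5.6.2 is applied to planned same-day samples, the two samples tie on study day and the later one is kept.
- Weeks 2 to 12: 4 of 8 kept.
- Day 1: the tie rule picks the second postdose sample, so 5 of 10 are kept and 5 left out. If SAP 5.5 makes the row predose, 4 of 10 are kept and 6 left out.
- If both samples enter each row instead, none are lost at Weeks 2 to 12, and the mixing in step 3 is unchanged.

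**The case against.** **The selection rule may not be meant for PK.** SAP 5.6.2 measures distance in days, which suits repeat or unscheduled visits and cannot separate samples taken hours apart. Read the same way, it would keep one of three triplicate ECGs, yet protocol 6.3.4 averages all legible ECGs at such visits. This stands. A reader might infer that the plan discards half of the postdose samples; the documents support that only under the literal reading. The mixing does not depend on it.

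**Day 1 is partly settled.** Protocol 9.5.3 separates before and after dosing, SAP 20 declares no change from the protocol's analyses, and SAP 5.5 defines Baseline as predose. This also stands. What remains is one unsplit row label in Table 2.

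**Consequences are limited.** No hypothesis is tested, all concentrations are listed, and the population PK analysis has its own plan and report. The interim PK analysis, on all available PK data, is also separate. Sparse sampling in intervals suits a population model. This stands and keeps the point minor. It does not make the summary interpretable, and population PK is a different endpoint.

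**Table specifications may already add time points.** Possible, but they were not available here. The SAP's stated rule points to visit alone, so correct tables would have to depart from it or add to it.

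**The figures rest on assumptions.** True of the slow-phase share, the interval choice and the sampling times. Doses also rise over visits, so equal exposure is a device to isolate the effect of timing. The extreme pair is the least favourable comparison, so the two-visit figures are given first.

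**Conclusion.** The plan is wrong as written on a minor point. SAP 16 with SAP 5.6 defines a by-visit concentration summary that ignores time after dose, under a sampling scheme in which that time varies between girls at the same visit. Week 2 to Week 12 rows have no defined postdose time. For 10 girls, sampling time alone would separate two given visit means by a median of about 1.4- to 1.3-fold, and the extreme pair of four by 2.1- to 1.7-fold. These sizes assume a slow-phase share of 5% to 20%, random compliant interval choice and equal exposure. The mixing itself needs only that girls at one visit are not all in the same interval.

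The loss of 5 or 6 of 10 scheduled postdose samples from the summary is conditional on reading SAP 5.6.2 literally.

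Two stronger inferences are not supported. The PK objective as a whole is not undermined, because listings and the separate population PK and interim PK reports are untouched. Nor is it a defect that girls on different doses share a row: visit rows follow the titration, and protocol 1.4.2 chose 5 g and 6 g to reach target exposure in each weight band.

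**What to change.** - In SAP 5.6.2, state that the one-record rule does not apply to planned PK samples.
- In SAP 16, summarise concentration by visit and time after dose: on Day 1, predose, 2 h and later postdose; at Weeks 2 to 12, the intervals 1-3, 4-7 and 8-11 h. Show the number of girls and the number of samples. This also resolves the single Baseline (Day 1) row.
- Use one value per girl per cell for mean, SD and SE, so that two correlated samples do not count as independent. Either average her two samples, or report first and second samples in separate rows.
- State that additional samples triggered by an SAE or AE are listed only, as an explicit exception to SAP 5.6.1, because their time after dose is not planned.

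The cost is SAP wording and table specifications. Sample and dosing times are already recorded (protocol 6.6 and 6.6.2), and no visit or sample changes.

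The downside is small cells. The 12 interval-by-visit cells hold on average 10/3 = 3.3 girls of 10, or 15/3 = 5 of 15. Under random compliant assignment, about 74% of draws with 10 girls and 21% with 15 have at least one cell with 0 or 1 girl. Individual values should therefore be shown beside the statistics.
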